## 6. STATISTICAL ANALYSIS PLAN

### 6.1. Analysis Populations

The ITT population consists of those subjects who have signed the Informed Consent Form and had the LIFESTREAM™ Covered Stent catheter introduced (i.e., delivery system enters the subject's body).

Subjects who do not receive the study implant (section 5.2.2), but the LIFESTREAM™ Covered Stent catheter was introduced will be included in the ITT population. Subjects who need more than two (2) LIFESTREAM™ Covered Stents (section 5.2.3) or undergo other treatment modalities (section 5.2.4) will be included in the ITT population.

A per-protocol (PP) population may be created if there are subjects who have any major protocol deviations. Major Protocol Deviations are defined as those that occur to protect the life or physical well-being of a subject in an emergency, or those that may affect the scientific soundness of the study, or the rights, safety or welfare of human subjects. The PP population will consist of any subjects in the ITT population who do not have any major protocol deviations, including deviations of study eligibility criteria. Subjects who do not receive the study implant (section 5.2.2), but the LIFESTREAM™ Covered Stent catheter was introduced will be included in the PP population. Subjects who need more than two (2) LIFESTREAM™ Covered Stents and require placement of a commercially-available stent (section 5.2.3), or undergo other treatment modalities (section 5.2.4) will be excluded from the PP population.

All effectiveness and safety analyses including the primary analysis will be primarily based on the ITT population. A PP analysis may also be performed for the primary endpoint. It will only serve as a sensitivity analysis for the primary analysis which is based on the ITT population.

### 6.2. Primary Endpoint: Study Hypothesis

The primary endpoint of the study is a composite safety and effectiveness measure defined as device and/or procedure-related death or MI through 30 days or any TLR, target limb(s) major amputation, or restenosis through 9 months post-index procedure.

The BOLSTER study is a single-arm study of treated subjects receiving the LIFESTREAM™ Covered Stent compared to a PG derived from published literature of stents for the treatment of iliac artery stenosis/occlusion. Specifically, the PG rate was derived as 19.5%.

The primary endpoint will be evaluated by the following hypothesis:

H0: The proportion of subjects in the LIFESTREAM™ Covered Stent group (PBBX) with events in the primary endpoint is greater than or equal to that of the PG of 19.5%.

H1: The proportion of subjects in the LIFESTREAM™ Covered Stent group (PBBX) with events in the primary endpoint is less than that of the PG of 19.5%.

$$\mathbf{H_0: P_{BBX} \geq 19.5\% \quad \text{vs.} \quad H_1: P_{BBX} < 19.5\%}$$

A one-sided p-value will be derived based on an exact binomial test. The study device will be considered to have achieved the primary objective if the one-sided p-value is less than 0.0335 at interim analysis or 0.0325 at final analysis (see section 6.8).

### **6.3. Assessment of Poolability of Sites**

The sites will be tested for potential differences in the primary endpoint. Sites with fewer than 10 treated subjects will be combined for this purpose. The pooling will be restricted within country. The sites with less than 10 treated subjects will be sorted by site number within each country and pooled by order to form one or more combined site(s) with at least 10 treated subjects. A logistic regression analysis will be performed with sites as a fixed effect. If the p-value associated with the sites effect is  $< 0.15$ , it will be considered as evidence of statistical significance.

If there are any site effects, the sites that have similar and dissimilar results will be grouped and exploratory analyses will be performed to investigate the potential reason for the differences among sites.

An analysis will be performed to examine the potential difference in the primary endpoint between the two geographic regions (US vs. OUS). A logistic regression model will be fit that includes fixed effect for geography. If the p-value of the geography effect is  $< 0.15$ , it will be considered evidence of a statistically significant difference between the geographic regions, and additional analyses will be performed to explore the differences between geographies to assess their potential causes and whether or not they are clinically meaningful.

Additionally, an analysis will be performed to explore the potential difference in the primary endpoint between males and females. If the p-value of the gender effect is  $< 0.15$ , it will be considered evidence of a statistically significant difference between the males and females.

### **6.4. Evaluation of Secondary Endpoints**

The following secondary endpoints are intended to be reported in the device's labeling and will be summarized using descriptive statistics. Kaplan-Meier survival analysis of the time to events will also be performed. The details of the definition of the secondary endpoints are described in Section 3.2.

- MAE
- Acute Lesion Success
- Acute Procedure Success
- Acute Technical Success
- TLR at 6-, 9-, 12-, 24-, and 36-months post-index procedure
- TVR at 6-, 9-, 12-, 24-, and 36-months post-index procedure
- Sustained Clinical Success at 30-days and 9-, 12-, 24-, and 36-months post-index procedure.
- Primary Patency at 9-, 12-, 24- and 36-months post-index procedure

- Primary Assisted Patency at 9-, 12-, 24-, and 36-months post-index procedure
- Secondary Patency at 9-, 12-, 24-, and 36-months post-index procedure
- Quality of Life at baseline, 30-days, and 9-, 12-, 24- and 36-months post-index procedure.

## 6.5. Exploratory Analyses

The primary endpoint and Primary Patency secondary endpoint will be explored in the following subgroups:

- Common iliac artery vs. external iliac artery
- Stenosis vs. occlusion
- TASC categories
- Unilateral vs. bilateral disease
- Gender

This information is intended to be reported in the device's labeling and will be summarized using descriptive statistics.

## 6.6. Handling of Missing Data

Study endpoints may be missing due to withdrawal of consent, investigator's decision, lost to follow-up and death. As long as the missing data is unrelated to the study intervention and the observed and unobserved data, limiting the analysis to those subjects who contribute endpoints produces unbiased estimates of the event rates.

Additionally, Kaplan-Meier survival analyses will be performed to estimate the event rates at various time-points. In survival analyses, unobserved endpoints are a standard part of the analysis. They are known as censored observations.

The reason for missing data for all subjects will be reported. If there is any indication that missing data is related to the study intervention, a worst-case analysis may be performed in addition to the standard analysis. In a worst-case analysis, a failure of effectiveness or safety will be assumed to have occurred at the time the subject was censored.

In addition, regardless of whether missing data are related to the study intervention, a tipping-point analysis will be performed, in which assumptions about missing data are varied from worst-case to best-case to examine at what point the missing data would alter the results of the analysis.

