## 6.7. Sample Size Determinations

The sample size calculation assumes the following:

1. The LIFESTREAM™ Covered Stent composite event rate is estimated at 10.5%
2. The PG is set at 19.5%

3. The Type 1 error,  $\alpha = 0.05$  (one-sided).
4. The Type 2 error,  $\beta = 0.10$  (Power =  $1 - \beta = 90\%$ ).

The calculated sample size is 139 subjects to be followed through the 9-month follow-up visit (using nQuery 7.0). To accommodate 10% censoring, the sample size is increased to 154.

Note, Bard estimates that 50% of consented subjects will not meet the eligibility criteria (e.g., Screen Failures), and therefore will not enter the analysis population. The estimated consented population will therefore be 308 [ $154 * 2 = 308$ ].

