### 6.8. Interim Analysis

An interim analysis will be performed when all of the first 103 enrolled subjects (at two thirds of the originally planned sample size) either complete the 9-month visits or discontinued from the study. The primary analysis at interim will be based on the first 103 enrolled subjects and no others whether or not there are additional subjects who may have completed their 9-month visits or discontinued at the time.

The linear alpha spending function will be used to control for the overall study-wise type I error rate of 0.05 (Proschan et al, 2006, Chapter 5 and 14). The null hypothesis will be rejected at interim based on  $n=103$  (93 evaluable) if the one-sided p-value is less than 0.0335 (calculated by R package ldbounds). If unsuccessful at interim, the null hypothesis will be rejected based on  $n=154$  (139 evaluable) if the one-sided p-value is less than 0.0325 (calculated by R package ldbounds).

A simulation study (Table 2) was performed to evaluate the operating characteristics of the procedure described above. Based on 100,000 simulations, the probability of achieving success at the interim analysis, the overall power of study (i.e., the probability of achieving success either at interim or at final analysis), and the probability of achieving success at interim but failing the final analysis were estimated with various assumptions of the composite event rate, including under the null hypothesis. Additionally, study power without an interim analysis was estimated as well for each of the scenarios.

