**Table 2: Simulation results**

True Event Rate	Interim Analysis (IA) success	Overall study power with IA	Reject at IA but fail at Final	Study power without IA
19.5%	1.8%	3.8%	0.8%	4.9%
12.5%	37.9%	64.7%	2.1%	71.7%
11.5%	49.1%	77.0%	1.6%	82.8%

10.5%	61.3%	87.1%	1.0%	91.1%
9.5%	73.3%	93.7%	0.5%	95.9%
8.5%	83.5%	97.5%	0.2%	98.6%
7.5%	91.1%	99.3%	0.1%	99.6%
6.5%	96.0%	99.9%	<0.1%	99.9%

When data were simulated under the null hypothesis, i.e., the composite event rate is 19.5%, there is a risk of 1.8% that the null hypothesis will be rejected falsely at interim and an overall false positive risk of 3.8%, which is below the study-wise type I error rate of 0.05.

When data were simulated under the alternative hypothesis, e.g., if the true composite event rate is 10.5% as originally assumed in the sample size calculation, there is a 61.3% chance the study will meet its primary objective at interim with two thirds of the planned sample size and a risk of 1.0% of failing the final analysis after declaring success at interim. By adding the interim analysis, the overall power of the study decreases slightly to 87.1% from the original designed 90% power. However, if the true composite event rate is a few percentage points better than originally assumed, for example at 8.5%, there is a 83.5% chance the study will declare success at interim and the overall power of the study is 97.5% with very little risk of achieving success at interim but failing at final analysis.

The simulation results show that the proposed interim analysis can potentially achieve study success faster with two thirds of the planned sample size, particularly if the true composite event rate is lower than originally assumed. It is unlikely that a final analysis would fail after success is achieved at interim. The added interim analysis may cause some loss of overall study power, but the amount of loss is small.

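### Section 6.6's condition for an unbiased complete-case rate generally cannot hold for an any-event-through-9-months composite on the natural counting rule; the effect is small and runs against the device

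*Combined protocol and SAP*

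**What the plan says.** - **Endpoint (Sections 3.1 and 6.2).** The composite is device- or procedure-related death or MI through 30 days, or any TLR, major amputation of a target limb, or restenosis through 9 months. It is tested as a proportion with a one-sided exact binomial test against 19.5%.
- **Missing data (Section 6.6).** Provided missingness is unrelated to the intervention and to observed and unobserved data, "limiting the analysis to those subjects who contribute endpoints produces unbiased estimates of the event rates". Kaplan-Meier analyses are additional. A worst-case analysis is optional and a tipping-point analysis is always done.
- **Sample size (Section 6.7).** The "Covered Stent composite event rate is estimated at 10.5" per cent. "The calculated sample size is 139 subjects to be followed through the 9-month follow-up visit", and "To accommodate 10% censoring, the sample size is increased to 154".
- **Interim (Section 6.8).** Success requires p < 0.0335 with 103 subjects (93 evaluable), or p < 0.0325 with 154 (139 evaluable). Below Table 2 the plan says that "the overall power of the study decreases slightly to 87.1% from the original designed 90% power".
- **Short follow-up (Sections 5.2.2 and 6.1).** Subjects in whom the catheter was introduced but no stent was implanted are followed to 30 days only and stay in the ITT population.

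The plan defines neither *evaluable* nor what it means to contribute an endpoint. It does not say how a subject with an event who later drops out is counted.

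**The concern.** The two outcomes of this endpoint become known at different times. Take two subjects who both withdraw at month 5 for reasons unrelated to their health. One had a TLR at month 3, so the endpoint is already a failure and the subject contributes it. The other had no event, so the 9-month status is unknown and the subject contributes nothing. Withdrawal was random, but whether the endpoint is missing depended on the outcome. The condition attached to the statement in Section 6.6 is then not met, and the complete-case proportion is too high on average.

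Subjects without an implant add to this. With follow-up ending at 30 days, they can contribute an early failure but never a 9-month success. Section 6.6 also lists death as a cause of missing endpoints, although a related death within 30 days is itself an endpoint event.

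At stake are the accuracy of the reported event rate and a small part of the power. Sections 6.7 and 6.8 treat the 10% censoring purely as a loss of subjects (154 to 139, 103 to 93) and leave the event rate among those analysed unchanged.

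**Working it through.** **1. Reproduce the plan's figures.** Inputs: goal 19.5%, assumed rate 10.5% and 10% censoring (Section 6.7); thresholds and evaluable numbers (Section 6.8).

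- Interim, n = 93: P(X ≤ 10 | 19.5%) = 0.0178 and P(X ≤ 11) = 0.0356, so success needs at most 10 events.
- Final, n = 139: P(X ≤ 18) = 0.0284 and P(X ≤ 19) = 0.0474, so success needs at most 18 events.
- Overall power = P(X₉₃ ≤ 10) + Σ P(X₉₃ = x) · P(X₄₆ ≤ 18 − x), summed over x = 11 to 18.

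| At a true rate of 10.5% unless noted | Exact | Plan |
|---|---|---|
| Interim success | 61.4% | 61.3% |
| Overall power | 86.9% | 87.1% |
| Power without interim (at most 19 of 139) | 90.9% | 91.1% |
| Overall rejection at 19.5% | 3.65% | 3.8% |

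Table 2 therefore applies the true rate unchanged to the evaluable subjects.

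**2. Expected rate under the natural counting rule.** Assumptions: 10% dropout, uniform over 9 months and independent of outcome. A share f of events is detected before the 9-month visit, spread evenly over the period. The rest are first found at that visit. The documents give no event timing, so f is varied.

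- An early event precedes dropout in half of the dropouts, so 0.90 + 0.10 × 0.5 = 0.95 of early events are retained.
- Events found at the visit are retained only in completers: 0.90.
- Event-free subjects are retained only if they complete: 0.90.

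With k = 0.95f + 0.90(1 − f):

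expected rate = p·k / [p·k + 0.90(1 − p)]

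Example, f = 0.5: k = 0.925, and the rate is 0.0971 / (0.0971 + 0.8055) = 10.76%.

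**3. Recompute power.** The rate from step 2 goes into the step 1 formula with 93 and 139 held fixed. The last column starts from p = 19.5%.

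| f | k | Expected rate | Overall power | Rejection when the true rate is 19.5% |
|---|---|---|---|---|
| 0 | 0.900 | 10.50% | 86.9% | 3.65% |
| 0.1 | 0.905 | 10.55% | 86.5% | 3.46% |
| 0.2 | 0.910 | 10.60% | 86.0% | 3.28% |
| 1/3 | 0.917 | 10.67% | 85.4% | 3.06% |
| 1/2 | 0.925 | 10.76% | 84.6% | 2.80% |
| 1 (limiting case) | 0.950 | 11.02% | 82.1% | 2.14% |

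The shift is small because few events are involved: 154 × 0.10 × 0.105 ≈ 1.6 events are expected among dropouts.

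**4. Random evaluable number.** Simulating 154 subjects with a random number evaluable gives 86.0% power if every dropout is excluded whatever happened earlier, and 81.4% in the limiting case. The loss is of the same order as with fixed numbers.

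**5. Plausible range of f.** Section 5.4 and Appendix 1 schedule duplex ultrasound at 30 days and then not until 9 months; month 6 is a telephone screen. Restenoses first seen at the 9-month scan do not count towards f. The limiting case would need practically no failure to be first found at that scan.

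**The case against.** A reader might infer that the plan keeps dropouts with events and removes the others, so that Section 6.6 is simply false and the stated power is not reached. The documents do not support that strength, for four reasons.

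- **The counting rule is an inference.** A symmetric rule that excludes every dropout, whatever happened before, would keep the expected rate at 10.5% and the fixed-n power at 86.9% under random dropout. This stands. But no such rule is written, and it would discard observed TLRs, amputations and related deaths from an ITT safety and effectiveness composite.
- **The sentence is conditional.** Read as a statement about missingness of the endpoint itself, it is correct. This also stands, so the criticism is that the condition generally cannot be met here, and the sentence reassures where it should not.
- **Safeguards exist.** Kaplan-Meier analyses are planned, and the best-case end of the mandatory tipping-point analysis, with all missing subjects event-free, bounds the upward bias. This stands in part. The tipping-point analysis probes the conclusion without correcting the reported rate. The Kaplan-Meier analysis has no stated time point, confidence limit or comparison with 19.5% for the primary composite.
- **The size depends on unstated timing.** With f up to one third, the rate moves by less than 0.2 points and power by about 1.5 points. About 0.2 points of any gap from 87.1% is the difference between simulated and exact results. Table 2 already shows power at worse true rates (77.0% at 11.5%), although it does not connect this with dropout.

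**Conclusion.** The point holds in a limited form. For this composite, the condition under which Section 6.6 calls the complete-case rate unbiased generally cannot hold on the ordinary reading of contributing an endpoint, even when dropout is random. With 10% uniform dropout, a true rate of 10.5% and 10% to 50% of events detected before the 9-month visit, the expected rate is about 10.55% to 10.8% and power about 86.5% to 84.6%, against an exact no-bias 86.9%. The limiting case is 11.0% and 82.1%. These figures rest on the inferred counting rule and on assumed event timing. They do not include the further contribution of subjects followed only to 30 days, whose number the documents do not give.

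A reader might also infer a threat to the validity of a positive result. There is none from this source: the bias works against the device, and the chance of a false success falls (from 3.65% to 2.1% in the limiting case). The cost is a slightly overstated event rate and a modest loss of power. This is a worthwhile improvement to the plan and not a serious flaw.

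**What to change.** 1. **Section 6.6:** replace the unbiasedness sentence with a statement that, for a composite settled by any earlier event, a complete-case proportion tends to overstate the rate even under random dropout.
2. **Section 6.1 or 6.6:** define *evaluable*. Say how subjects with an event before dropout are counted, and how ITT subjects without an implant, followed only to 30 days, are counted.
3. **Section 6.6:** specify that the Kaplan-Meier analysis already planned (or multiple imputation of event-free dropouts) provides the all-ITT estimate of the primary composite at the close of the 9-month window. Give it a one-sided upper confidence limit compared with 19.5%, and report it beside the exact test.
4. **Section 6.2:** keep the exact test as the decision rule and describe it as conservative in this respect.
5. **Section 6.8:** note that the Table 2 power assumes no event precedes dropout, and give the power range under stated timing assumptions.

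The cost is SAP wording and one further analysis of data already collected. There are no new visits or subjects, and the success criterion does not change. The quoted power becomes slightly less favourable.

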## 6.7. Sample Size Determinations

The sample size calculation assumes the following:

1. The LIFESTREAM™ Covered Stent composite event rate is estimated at 10.5%
2. The PG is set at 19.5%

3. The Type 1 error,  $\alpha = 0.05$  (one-sided).
4. The Type 2 error,  $\beta = 0.10$  (Power =  $1 - \beta = 90\%$ ).

The calculated sample size is 139 subjects to be followed through the 9-month follow-up visit (using nQuery 7.0). To accommodate 10% censoring, the sample size is increased to 154.

Note, Bard estimates that 50% of consented subjects will not meet the eligibility criteria (e.g., Screen Failures), and therefore will not enter the analysis population. The estimated consented population will therefore be 308 [ $154 * 2 = 308$ ].

### 6.8. Interim Analysis

An interim analysis will be performed when all of the first 103 enrolled subjects (at two thirds of the originally planned sample size) either complete the 9-month visits or discontinued from the study. The primary analysis at interim will be based on the first 103 enrolled subjects and no others whether or not there are additional subjects who may have completed their 9-month visits or discontinued at the time.

The linear alpha spending function will be used to control for the overall study-wise type I error rate of 0.05 (Proschan et al, 2006, Chapter 5 and 14). The null hypothesis will be rejected at interim based on  $n=103$  (93 evaluable) if the one-sided p-value is less than 0.0335 (calculated by R package ldbounds). If unsuccessful at interim, the null hypothesis will be rejected based on  $n=154$  (139 evaluable) if the one-sided p-value is less than 0.0325 (calculated by R package ldbounds).

A simulation study (Table 2) was performed to evaluate the operating characteristics of the procedure described above. Based on 100,000 simulations, the probability of achieving success at the interim analysis, the overall power of study (i.e., the probability of achieving success either at interim or at final analysis), and the probability of achieving success at interim but failing the final analysis were estimated with various assumptions of the composite event rate, including under the null hypothesis. Additionally, study power without an interim analysis was estimated as well for each of the scenarios.

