Enrollment:	
Enrollment will continue until one-hundred fifty-four (154) subjects are treated with the LIFESTREAM™ Balloon Expandable Vascular Covered Stent, which is an estimated three-hundred eight (308) consecutive subjects in a non-randomized fashion.
 
Subjects will be considered enrolled in the study at the time the informed consent document is signed (an estimated 308 subjects). After the subject has met all eligibility criteria, undergone successful PTA of the target lesion(s), and the LIFESTREAM™ Balloon Expandable Vascular Covered Stent catheter is introduced (i.e. delivery system enters the subject’s body), the subject will enter the primary analysis population (up to 154 subjects).
																																								

Investigational Sites:	Up to thirty-five (35) sites will be utilized for this study throughout the United States (U.S.), Europe, and Australia/New Zealand.
Study Population:	Subjects will be males or non-pregnant females, at least 21 years of age, with an expected lifespan sufficient to allow for completion of all study procedures. Eligible subjects will have intermittent claudication or ischemic rest pain and angiographic confirmation of either de novo or restenotic (non-stented) lesion(s) $\geq 50\%$ in the common and/or external iliac arteries.

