### 4.2. Number of Subjects

Enrollment will continue until 154 subjects are treated with the LIFESTREAM™ Covered Stent, which is an estimated 308 consecutive subjects in a non-randomized fashion (See Section 5.2.2).

No more than 31 (~20%) treated subjects may be enrolled at any site. Each site is anticipated to enroll a minimum of 3 treated subjects; sites with fewer than 10 treated subjects will be pooled for analysis (see Section 6.3). It is anticipated that the required 154 treated subjects will be enrolled over a 12-month timeframe.

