### 4.3. Eligibility Criteria

#### 4.3.1. Inclusion Criteria

A subject must meet the following criteria to be enrolled and considered a treated subject in the study:

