**It is required that angiographic image(s) of the inflated PTA balloon be captured.**

Choice of specific balloon catheters and inflation pressure should be determined by the Investigator based on his/her standard of care practices, and should be recorded. It is **not** acceptable for the Investigator to use additional commercially-approved treatment modalities (e.g., atherectomy, cryotherapy, cutting/scoring balloon) during the study procedure. Subjects who require treatment with any of these alternative modalities should not be enrolled in the study. It is acceptable for the Investigator to use CTO catheters or re-entry devices to facilitate target lesion(s) crossing.

In certain instances, a dissection may occur following PTA of the target lesion(s).

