## 5.2.2. Enrollment

### Enrollment

A subject is considered enrolled in the study once he/she has agreed to study participation and has provided consent (an estimated 308 subjects assuming a 50% screen failure rate). Subjects who fail to meet eligibility criteria should be treated according to the Investigator's standard of care practices. Such subjects' study participation will end at the time of eligibility failure.

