## 7. CLINICAL EVENT REPORTING

The Principal Investigator (PI), or authorized designee, is responsible for the detection and documentation of events meeting the criteria and definitions set forth in Section 7.1. Collection of these events will begin immediately following subject enrollment (events occurring prior to becoming a treated subject as defined in 5.2.2 will be documented as medical history), during the index procedure through final subject follow-up visit or early termination.

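### Does the interim analysis count 103 consented subjects or 103 treated subjects?

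*Combined protocol and SAP*

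**What the plan says.** Section 6.8 sets the interim trigger on the "first 103 enrolled subjects (at two thirds of the originally planned sample size"), once each has completed the 9-month visit or discontinued. It then locks the data set: "The primary analysis at interim will be based on the first 103 enrolled subjects and no others". The section restates the look as n=103 with 93 evaluable, against n=154 with 139 evaluable at the final analysis, with one-sided thresholds of 0.0335 and 0.0325.

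Section 5.2.2 gives the formal definition: "A subject is considered enrolled in the study once he/she has agreed to study participation and has provided consent". The Clinical Protocol Summary agrees and puts the expected number at 308. Section 5.2.2 defines a treated subject separately, as one who met eligibility, had successful PTA and had the stent catheter introduced. Section 7 keeps the two stages apart as well: "events occurring prior to becoming a treated subject as defined in 5.2.2 will be documented as medical history".

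Other sections use the word more loosely. Section 4.2: "It is anticipated that the required 154 treated subjects will be enrolled over a 12-month timeframe". Section 4.3.1: "A subject must meet the following criteria to be enrolled and considered a treated subject in the study". Section 5.2.1, describing a decision made at the PTA stage and so after consent: "Subjects who require treatment with any of these alternative modalities should not be enrolled in the study".

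**The concern.** The sentence selects the data for a look that can declare the trial a success, and it bars substitution. Its governing word is a defined term, and under the definition it names the wrong people. Of 308 expected consents, 103 is 33%, not two thirds.

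The literal reading could even be carried out. Section 5.2.2 ends a screen failure's participation when eligibility fails, so such a subject might be counted as discontinued and satisfy the trigger while adding nothing to the ITT analysis. If the look were taken that way, the interim sample would be about half the size intended, interim success would be much less likely than Table 2 shows, and 0.0335 would be spent at an information fraction of about one third instead of two thirds.

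**Working it through.** **Inputs.** From 6.7: performance goal 19.5%, assumed event rate 10.5%, overall one-sided alpha 0.05, 139 evaluable, 10% censoring, 154 treated, 50% screen failure, 308 consented. From 6.2 and 6.8: exact binomial test, linear spending, thresholds 0.0335 and 0.0325.

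**1. Which count gives the stated sizes?**
- Treated: 154 × 2/3 = 102.7, so 103. Evaluable: 103 × 0.9 = 92.7, so 93; 154 × 0.9 = 138.6, so 139.
- Consented: two thirds of 308 is 205, not 103. From 103 consents, 103 × 0.5 = 51.5 treated, and 51.5 × 0.9 = 46.35, so 46 evaluable.

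Going from 103 to 93 uses up the 10% censoring allowance exactly. It leaves no room for screen failures.

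**2. Which count gives the stated thresholds?** Under linear spending the interim level is 0.05 × information fraction.
- 93/139 = 0.669: 0.05 × 0.669 = 0.03345, rounding to 0.0335. The matching final nominal level is 0.03246, rounding to 0.0325. Both agree with 6.8.
- 46/139 = 0.331: interim 0.0165 and final 0.0392. Neither agrees.

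**3. Which count gives Table 2?** With n=93 the largest event count giving p < 0.0335 is 10; with n=139 the largest giving p < 0.0325 is 18. Overall success = P(X₉₃ ≤ 10) + P(X₉₃ > 10 and X₁₃₉ ≤ 18).

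| True rate | Interim success, exact (Table 2) | Overall success, exact (Table 2) |
|---|---|---|
| 19.5% | 1.78% (1.8%) | 3.65% (3.8%) |
| 12.5% | 37.55% (37.9%) | 64.53% (64.7%) |
| 11.5% | 49.16% (49.1%) | 76.97% (77.0%) |
| 10.5% | 61.42% (61.3%) | 86.92% (87.1%) |
| 9.5% | 73.24% (73.3%) | 93.71% (93.7%) |
| 8.5% | 83.44% (83.5%) | 97.55% (97.5%) |
| 7.5% | 91.15% (91.1%) | 99.26% (99.3%) |
| 6.5% | 96.10% (96.0%) | 99.84% (99.9%) |

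The largest gaps are 0.35 points (interim) and 0.18 points (overall).

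**4. The literal reading, for comparison.** With 46 evaluable and the 0.0335 threshold kept, the cut-off is 3 events. At 10.5%, interim success is 27.45% and overall power 86.58%; at 19.5%, overall error is 3.80%. Assuming screen-failure rates from 20% to 60%, 103 consents give 74 down to 37 evaluable, and interim success at 10.5% runs from 48% down to 24%. No value in that range gives 93 evaluable or 61.3%.

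**5. Which subjects can enter the analysis?** Section 6.1 bases the primary analysis on the ITT population, meaning consent plus catheter introduced. Section 6.7 states that screen failures do not enter the analysis population, and it treats 154 as the sample size and 308 as the expected number of consents. An interim primary analysis on 103 subjects therefore means 103 treated subjects.

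**The case for a change.** The strongest case is that a rule which locks the data set for an early success claim should not depend on inference, least of all when its key word is defined elsewhere to mean something different. The literal reading can be carried out, and in normal theory, spending 0.0335 at a fraction of 0.33 and then 0.0325 at the end gives an overall error of 0.0576, against 0.0501 at two thirds. Even once *treated* is understood, *first* could follow consent date or procedure date, and Section 2 describes the timing as 103 subjects followed for 9 months, without the allowance for discontinuation.

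What stands is that the word is used in two senses. The rest carries little weight. The test is exact, and its discreteness keeps overall error at 3.80% even under the literal reading, with overall power at 86.6% against 86.9%. Consent date and procedure date both precede follow-up outcomes, and no effect of choosing one over the other has been shown; it could matter only for subjects near the 103rd place. Section 2 is a one-line summary that names no competing analysis set, and 6.8 gives the operative completion rule.

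**Conclusion.** No change to the plan follows. Section 6.8 uses a defined term loosely, as Sections 4.2, 4.3.1 and 5.2.1 also do, but it states beside the word which denominator applies. Sample sizes, thresholds and Table 2 all agree on 103 treated subjects with 93 evaluable, and Sections 6.1 and 6.7 exclude anyone else from the analysis. An analyst building the interim data set would reach that reading without having to choose between live alternatives.

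Under it, interim success at a 10.5% event rate is 61.4% (stated 61.3%), overall power 86.9% (87.1%) and overall type I error 3.65% (3.8%). Substituting the word would alter none of these figures, nor the subjects analysed. The 27.5% interim success figure belongs only to a reading that the section's own numbers rule out. These results assume the evaluable counts the plan states, 93 and 139; the literal comparison also assumes the plan's 50% screen-failure and 10% censoring rates.
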